#### **7.4.2 Analysis of Secondary Endpoints**

Refer to Section 10.2 Appendix 2. They include categorical, continuous, and time-to-event variables, with "X" indicating that the variable will be analyzed. As for secondary variables, no multiplicity adjustment will be done. Basically, analysis of secondary endpoints except for mTSS, erosion score, and joint space narrowing score will be performed by Initial Randomization Set and Treatment Sequence Set defined at Section 7.1.

The secondary variables and analyses are as follows:

<Initial Randomization Set>

- Categorical variables at each visit (including Baseline, Weeks 4, 8, 12, 12/ET, Week 28/ET) will be analyzed using Fisher's exact test, as described for the primary efficacy variable, unless otherwise specified in Section 10.2 Appendix 2.
- Raw value and change from baseline variables at each visit (Baseline, Weeks 4, 8, 12, 12/ET, Week 28/ET) will be analyzed using the ANCOVA model with fixed effects for treatment, and baseline value as a covariate.
- Time to the first response analysis will be analyzed similarly as described in 7.4.1.5.
  - ACR50-CRP
  - ACR70-CRP
  - DAS28-CRP <2.6
  - SDAI score <= 3.3
  - CDAI score <= 2.8
  - ACR/EULAR score for remission

As for DAS28-CRP < 2.6, CDAI score <= 2.8, SDAI score <= 3.3, ACR/EULAR score for remission, if the event is occurred at baseline, then that subject is excluded from this analysis.

- Graphical analysis (including Baseline, Weeks 4, 8, 12, 12/ET, Week 28/ET).
  - ACR20/50/70-CRP will be plotted for over time.
  - The mean-standard deviation plot of actual values and changes from baseline will be presented for DAS28-CRP and DAS28-ESR.
  - To visually explore possible relationships between ACR20-CRP and DAS28-CRP, 2-panel line graphs of DAS28-CRP over time will be plotted for ACR20-CRP responders (in 1 panel) and non-responders (in another panel). Similar graphs will be provided for DAS28-ESR.

<Treatment Sequence Set>

- Categorical variables at each visit (including Baseline, Weeks 4, 8, 12, 16, 20, 24, 28, 32, 36, 40, 44, 48, 52, EOT) will be summarized as described in Section 10.2 Appendix 2.
- Raw value and change from baseline variables at each visit (including Baseline, Weeks 4, 8, 12, 16, 20, 24, 28, 32, 36, 40, 44, 48, 52, EOT) will be summarized by descriptive statistics.
- Graphical analysis (including Baseline, Weeks 4, 8, 12, 16, 20, 24, 28, 32, 36, 40, 44, 48, 52, EOT).
  - ACR20/50/70-CRP will be plotted for over time.
  - The mean-standard deviation plot of actual values and changes from baseline will be presented for DAS28-CRP and DAS28-ESR.

<mTSS, Erosion Score, and Joint Space Narrowing Score>

In this analysis, mTSS, Erosion Score, and Joint Space Narrowing Score will be imputed using linear extrapolations as described in the primary analysis.

- Categorical variables at each visit (including Week 28/ET, Week 52/ET) will be analyzed using Fisher's exact test.
  - mTSS change from baseline  $\geq 3$
  - mTSS change from baseline  $\leq 0.5$
  - mTSS change from baseline  $\leq 0$
- Yearly progression of mTSS will be analyzed
- Percentage of subjects showing Rapid Radiographic Progression: RRP (Yearly progression of mTSS  $\geq 5$ )
- Raw value and change from baseline variables at each visit (including Week 28/ET, EOT) will be analyzed using the RANCOVA model with treatment group (Placebo, ASP015K 100 mg, ASP015K 150 mg) as factor and baseline rank mTSS as covariate.
  - mTSS (Week 52/ET)
  - Erosion Score (Week 28/ET, Week 52/ET)
  - Joint Space Narrowing Score (Week 28/ET, Week 52/ET)
- Graphical analysis (including Week 28/ET, Week 52/ET).
  - Cumulative probability plot for the change from baseline in mTSS score, Erosion Score, Joint Space Narrowing Score will be presented at Week 28/ET, Week 52/ET.
  - Scatter plot for mTSS score at baseline to mTSS at Week 28/ET, Week 52/ET will be presented.
  - Scatter plot for mTSS score at baseline to mTSS change from baseline at Week 28/ET, Week 52/ET will be presented.

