7.4.2 Analysis of Secondary Variables

For secondary efficacy endpoints, binary variables such as Percentage of subjects achieving ACR50 response at Week 12/ET, Percentage of subjects achieving ACR70 response at Week 12/ET will be analyzed using Fisher's exact test, and continuous variables, such as Change from baseline/Day 1 to Week 12/ET in DAS28-CRP and DAS28-ESR scores, will be analyzed using ANCOVA with treatment group as factor and baseline as covariate. Each ASP015K group will be compared with placebo group and multiplicity for the secondary efficacy variables will not be adjusted.

- CONFIDENTIAL -

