  - SJC (28 joints)
  - SGA (0-10 cm VAS)
  - PGA (0-10 cm VAS)
  - CRP (mg/dL)

$$\text{SDAI} = \text{TJC} + \text{SJC} + \text{SGA} + \text{PGA} + \text{CRP}$$

Note: If any component is a missing value, then SDAI score will be a missing value.

- Percentage of subjects with a CDAI score of  $\leq 2.8$  at each analysis visit  
CDAI score is consist of following parameters, and calculated according to below description.
  - TJC (28 joints)
  - SJC (28 joints)
  - SGA (0-10 cm VAS)
  - PGA (0-10 cm VAS)

$$\text{CDAI} = \text{TJC} + \text{SJC} + \text{SGA} + \text{PGA}$$

Note: If any component is a missing value, then CDAI score will be a missing value.

- Percentage of subjects achieving HAQ-DI ( $\leq 0.5$ ) at each analysis visit
- Percentage of subjects achieving decrease of baseline HAQ-DI of at least 0.22 at each analysis visit
- Percentage of subjects achieving SF-36v2 of difference  $\geq 5$  at each analysis visit

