**Table15. Overview of Secondary Endpoints analysis**

Analysis Type/Analysis Variable 		CRP	ESR	None	Treatment Group	Analysis Method 
Categorical Variables						
1.1.1	Percentage of subjects achieving ACR20/50/70 at each visit (Weeks 4, 8, 12, 12/ET,28/ET)	X	X		Placebo, 100mg, 150mg	
 
Fisher's exact test.
 
ACR20-CRP at Week 12/ET is not displayed in this analysis.
 

1.1.2	Percentage of subjects achieving ACR20/50/70 at each visit (Weeks 4, 8, 12, 16, 20, 24, 28, 32, 36, 40, 44, 48, 52, EOT)	X			100mg, 150mg, Placebo to 100mg at Week 12, Placebo to 150mg at Week 12, Placebo to 100mg at Week 28, Placebo to 150mg at Week 28	No statistical test
1.2.1	Line graph of 1.1.1	X	X		Placebo, 100mg, 150mg	No statistical test
1.2.2	Line graph of 1.1.2	X			100mg, 150mg, Placebo to 100mg at Week 12, Placebo to 150mg at Week 12, Placebo to 100mg at Week 28, Placebo to 150mg at Week 28	No statistical test.
2.1	Percentage of subjects achieving ACR20 response at Week 4 and sustaining response at each visit (Week 8, 12)	X			Placebo, 100mg, 150mg	Fisher's exact test.
2.2	Percentage of subjects achieving ACR20 response at Week 8 and sustaining response at Week 12	X			Placebo, 100mg, 150mg	Fisher's exact test.
3.1	Percentage of subjects achieving DAS28 score < 2.6 at each visit (Baseline, Week 4, 8, 12, 12/ET, 28/ET)	X	X		Placebo, 100mg, 150mg	Fisher's exact test.
3.2	Percentage of subjects achieving DAS28 score < 2.6 at each visit (Baseline, Weeks 4, 8, 12, 16, 20, 24, 28, 32, 36, 40, 44, 48, 52, EOT)	X	X		100mg, 150mg, Placebo to 100mg at Week 12, Placebo to 150mg at Week 12, Placebo to 100mg at Week 28, Placebo to 150mg at Week 28	No statistical test.
3.3	Percentage of subjects achieving DAS28 score	X	X		Placebo, 100mg, 150mg	Fisher's exact test.

	<=3.2 at each analysis visit					
3.4	Percentage of subjects achieving DAS28 score <=3.2 at each analysis visit	X	X		100mg, 150mg	No statistical test.
4.1	Percentage of subjects achieving "Good Response" using DAS28 EULAR response criterion at each visit (Baseline, Week 4, 8, 12, 12/ET,28/ET)	X	X		Placebo, 100mg, 150mg	Fisher's exact test.
4.2	Percentage of subjects achieving "Good Response" using DAS28 EULAR response criterion at each visit (Baseline, Weeks 4, 8, 12, 16, 20, 24, 28, 32, 36, 40, 44, 48, 52, EOT)	X	X		100mg, 150mg	No statistical test.

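### The secondary threshold endpoints on HAQ-DI, DAS28, SDAI and CDAI are compared by unadjusted Fisher's exact test; using the baseline score already collected would gain precision at little cost

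*SAP*

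**What the plan says.** In SAP 7.4.2, for the comparison of the three randomised arms, categorical variables at each visit are analysed by Fisher's "exact test, as described for the primary efficacy variable, unless otherwise specified in Section 10.2 Appendix 2". Appendix 2 repeats Fisher's test, with no covariate, for DAS28 (items 3.1 and 3.3), SDAI (7.1), CDAI (8.1) and HAQ-DI ≤0.5 (9.1). The last is listed in SAP 6.1.2.1 as "Percentage of subjects achieving HAQ-DI" at or below 0.5. Item 3.1 reads "Percentage of subjects achieving DAS28 score < 2.6 at each visit (Baseline, Week 4, 8, 12, 12/ET, 28/ET", so the Baseline visit is among those covered.

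For the continuous forms, SAP 7.4.2 says that they "will be analyzed using the ANCOVA model with fixed effects for treatment, and baseline value as a covariate". A footnote to Appendix 2 limits this model to the change score. Protocol 7.4.2 agrees: "continuous variables, such as Change from baseline/Day 1 to Week 12/ET in DAS28-CRP and DAS28-ESR scores, will be analyzed using ANCOVA". Protocol 7.4.2 also assigns Fisher's test to binary secondary variables, with ACR50 and ACR70 as its examples.

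A covariate-adjusted treatment comparison of a binary endpoint is planned only for primary ACR20, and only if baseline imbalance is found (SAP 7.4.1.4).

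**The concern.** Each of these endpoints asks whether a score is below a cut-off at follow-up. Where the baseline score predicts the follow-up score, it also predicts which side of the cut-off a subject ends on. The plan uses that information for the change score and not for the threshold. The randomisation sections (Protocol 4.5, SAP 3.3) describe no stratification by disease score, so chance imbalance in baseline score passes directly into the unadjusted comparison.

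What is at stake is precision. These comparisons carry no multiplicity adjustment, so their value lies mainly in estimation, and an adjusted estimate would be tighter for data already in hand.

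**Working it through.** **1. The plan's own figure.** The 151 per group comes from mTSS, not from these endpoints; it matters here only because it fixes the arm size. With a difference of 2.0 − 0.5 = 1.5, SD 4.0, two-sided 5% and 90% power, the normal formula gives n = 2(1.960 + 1.282)² × 4.0² / 1.5² ≈ 150. The noncentral t gives 89.9% power at 150 and 90.1% at 151, so 151 reproduces. 151/0.9 = 167.8, hence 168, planned as 170.

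**2. Conservatism of Fisher's test.** Its exact two-sided size at 170 per arm, nominal 5%, is 2.6%, 3.2%, 3.6%, 3.8% and 3.6% at null rates of 5%, 10%, 20%, 30% and 50%.

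**3. Value of the baseline score.** Assumptions, none of them in the documents: the response rates, a normal latent follow-up score cut at a threshold, and its correlation with baseline. There were 170 per arm and 4,000 replicates per row. Pearson's test is included because its size is close to that of the adjusted test, so the two sources of loss can be separated. The variance ratio is that of the standardised risk difference, adjusted over unadjusted.

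| Rates | Correlation | Fisher | Pearson | Adjusted logistic | Variance ratio |
|---|---|---|---|---|---|
| 25% v 40% | 0 | 82.4% | 85.1% | 85.2% | 1.00 |
| | 0.3 | 82.2% | 85.0% | 86.4% | 0.960 |
| | 0.5 | 81.7% | 84.7% | 89.9% | 0.854 |
| | 0.7 | 82.1% | 84.9% | 94.9% | 0.698 |
| 10% v 20% | 0 | 69.3% | 74.3% | 74.6% | 1.00 |
| | 0.3 | 69.3% | 74.2% | 76.0% | 0.968 |
| | 0.5 | 69.5% | 74.2% | 79.3% | 0.881 |
| | 0.7 | 68.1% | 73.7% | 85.6% | 0.745 |

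- Pearson minus Fisher (conservatism): 2.7–3.0 points in the first block, 4.7–5.6 in the second.
- Adjusted minus Pearson (baseline): 1.4 and 1.8 points at 0.3; 5.2 and 5.1 at 0.5; 10.0 and 11.9 at 0.7.
- Type I error, at null rates of 25% and 10%: Fisher 2.9–4.3%, Pearson 4.7–5.7%, adjusted 4.7–5.6%.

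A separate simulation at 170 per arm gave about 4–5 points for conservatism and 1–2, 5–6 and 11–14 for baseline. It put the variance reduction at 6–8%, 10–16% and 27–31%, against 3–4%, 12–15% and 25–30% in the table.

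**4. Does the gain hold when the p-value comes from the risk difference?** The adjusted column used a likelihood ratio test. For 25% v 40%, the unadjusted SE is √[(0.25×0.75 + 0.40×0.60)/170] = 0.0501, so z = 0.15/0.0501 = 2.99 and power is Φ(2.99 − 1.96) = 85%. Dividing z by the square root of the variance ratio gives 3.05, 3.24 and 3.58 at the three non-zero correlations, that is, power of 86%, 90% and 95%. This matches the table, so a test based on the standardised risk difference keeps the gain.

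**5. Dependence on the assumed effect.** For 26% v 36%, Fisher has 46–47% power and the adjusted model 57% at correlation 0.5. For 14% v 35%, the figures are 99% and above 99%, so little is left to gain.

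**The case against.** The strongest reply is that nothing is wrong. Fisher's test holds its level and is the protocol's test for binary secondary variables. The endpoints lie outside the four-step hierarchy, and baseline-adjusted analyses of the same scores as change from baseline are already planned. All of this stands, and it limits the point to efficiency.

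The size is also assumption-driven. For 14% v 26%, a check gave Fisher 76%, Pearson 80% and adjusted logistic 80–82% at correlation 0.2–0.3, against 85% at 0.5. If the correlation is weak, most of the gap is Fisher's conservatism. That stands too.

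A reader might infer three stronger points. The documents do not support them.

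- *The mTSS no-progression endpoints have the same weakness.* They are also unadjusted ("Categorical variables at each visit (including Week 28/ET, Week 52/ET) will be analyzed using Fisher's exact test"), while the continuous scores use treatment "as factor and baseline rank mTSS as covariate". But they are thresholds on change, not on a follow-up score. No document says that baseline mTSS predicts crossing them, and the gain could be near zero.
- *The SAP is inconsistent about subjects already at target.* For the time-to-event versions, "if the event is occurred at baseline, then that subject is excluded from this analysis". A subject already in the state has no time to first occurrence, so that rule belongs to the method. HAQ-DI, where entry at or below 0.5 is plausible because functional Class I is eligible and no minimum HAQ-DI is set, has no time-to-event version (SAP 6.1.2.3). For DAS28-CRP, the minimum entry values of 6 tender joints, 6 swollen joints and CRP 10 mg/L give 0.56√6 + 0.28√6 + 0.36 ln(11) + 0.96 = 3.88 before the subject's global assessment is added, already above both targets. This is indicative only, because entry counts use 68/66 joints at screening.
- *Efficacy claims rest on these tests.* The confirmatory claims rest on ACR20 and mTSS change, which this point leaves untouched.

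**Conclusion.** The point holds as a cheap improvement for HAQ-DI ≤0.5, DAS28 <2.6 and ≤3.2, SDAI ≤3.3 and CDAI ≤2.8. Taking both simulations together, Fisher's conservatism costs about 3–6 power points. Ignoring baseline costs about 1–2, 5–6 or 10–14 more at a correlation of 0.3, 0.5 or 0.7, with the risk-difference variance lower by about 3–8%, 10–16% or 25–31% when baseline is used. These figures rest on assumed rates, assumed correlations and a normal latent score. They shrink towards zero when the correlation is weak, and the power gain also shrinks when power is already near 100%. Validity, sample size and the primary tests are unaffected.

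**What to change.** In SAP 7.4.2 and Appendix 2 items 3.1, 3.3, 7.1, 8.1 and 9.1:

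- For post-baseline visits only, use logistic regression with treatment and the continuous baseline value of the same score. The Baseline visit must be left out: the baseline score determines the baseline threshold exactly, so the model would separate perfectly.
- Report the standardised risk difference with its 95% CI, and take the p-value from that same estimate so that test and interval agree. The conditional odds ratio should not be the headline, because the precision gain appears on the marginal scale.
- Keep Fisher's exact test as the prespecified supportive analysis.
- List by endpoint, in advance, those expected to be sparse (such as the remission targets), which keep the exact test or use Firth logistic regression. Do not switch method on observed counts.

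The cost is SAP wording and standard code; logistic regression is already used elsewhere in the SAP. The departure from the protocol's exact test must be noted, and sparse endpoints need the stated fallback. The change must be made before unblinding, as the SAP requires of its own finalisation.

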### **Change from baseline in mTSS at Week 28 or early termination (Week 28/ET) (suppression of joint destruction)**

The severity of joint destruction in hands and feet (bone erosion and joint fissure narrowing) will be assessed by the third party through the mTSS method by scoring the severity of bone erosion and joint fissure narrowing of the target joints and calculate the total score. The target joints and the scoring method are described in the SOP prepared by the third party institution.

The results of the assessment will be sent to the sponsor by the third party institution.

The higher scores in mTSS represent greater damage and the positive change from baseline in mTSS represents unfavorable values.

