10.2	Percentage of subjects showing no progression of joint damage (mTSS change from baseline $\leq$ 0) at each visit (Baseline, Week 28/ET, EOT)			X	Placebo, 100mg, 150mg	Fisher's exact test.
10.3	Percentage of subjects showing Clinically Relevant Radiographic Progression: CRRP (mTSS change from baseline $\geq$ 3) at each analysis visit			X	Placebo, 100mg, 150mg	Fisher's exact test.
10.4	Percentage of subjects showing Rapid Radiographic Progression: RRP (Yearly progression of mTSS $\geq$ 5)			X	Placebo, 100mg, 150mg	Fisher's exact test.

11.1	Percentage of subjects achieving SF-36v2 of difference $\geq 5$ at each visit (Weeks 4, 8, 12, 12/ET, 28/ET)	X			Placebo, 100mg, 150mg	Fisher's exact test.
11.2	Percentage of subjects achieving SF-36v2 of difference $\geq 5$ at each visit (Weeks 4, 8, 12, 28, 52, EOT)	X			100mg, 150mg	No statistical test.
Continuous Variables						
12.1.1	Raw value and change from baseline in mTSS score at each visit (Baseline, Week 52/ET)			X	Placebo, 100mg, 150mg	Descriptive Statistics RANCOVA  analysis with Week 52/ET. No multiplicity adjustment.
12.1.2	Raw value and change from baseline in Erosion Score at each visit (Baseline, Week 28/ET, Week 52/ET)			X	Placebo, 100mg, 150mg	Descriptive Statistics; RANCOVA  analysis with each visit. No multiplicity adjustment.
12.1.3	Raw value and change from baseline in Joint Space Narrowing Score at each visit (Baseline, Week 28/ET, Week 52/ET)			X	Placebo, 100mg, 150mg	Descriptive Statistics; RANCOVA  analysis with each visit. No multiplicity adjustment.
12.2.1	Cumulative probability plot for the change from baseline in mTSS score at Week 52/ET			X	Placebo, 100mg, 150mg	
12.2.2	Cumulative probability plot for the change from baseline in Erosion Score at Week 28/ET, Week 52/ET			X	Placebo, 100mg, 150mg	
12.2.3	Cumulative probability plot for the change from baseline in Joint Space Narrowing Score at Week 28/ET, Week 52/ET			X	Placebo, 100mg, 150mg	
12.3.1	Scatter plot for mTSS score at baseline to Week 28/ET, Week 52/ET			X	Placebo, 100mg, 150mg	
12.3.2	Scatter plot for mTSS score at baseline to mTSS change from baseline at Week 28/ET, Week 52/ET			X	Placebo, 100mg, 150mg	
12.4.1	Yearly Progression of mTSS			X	Placebo, 100mg, 150mg	Descriptive Statistics;
13.1.1	Raw value and change from baseline in DAS28	X	X		Placebo, 100mg, 150mg	Descriptive Statistics;

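### Erosion and joint-space-narrowing changes should be adjusted for the rank of their own baseline score, not baseline mTSS rank: a free correction with a probably small gain

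*SAP*

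**What the plan says.** SAP 7.4.2 has a separate block for the three radiographic scores. It sets one rank ANCOVA model with treatment group "as factor and baseline rank mTSS as covariate". The scores listed under it are mTSS at Week 52/ET, "Erosion Score (Week 28/ET, Week 52/ET") and "Joint Space Narrowing Score (Week 28/ET, Week 52/ET"). The covariate is the one used for the primary mTSS analysis in SAP 7.4.1.1.

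SAP Appendix 2 does not change this. Row 12.1.2, "Raw value and change from baseline in Erosion Score at each visit (Baseline, Week 28/ET, Week 52/ET"), and row 12.1.3 for joint-space narrowing give the method only as RANCOVA. The footnote on the method column sends the reader back to 7.4.2 for model details.

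The general rules are worded differently. In protocol 7.4.2, continuous secondary endpoints "will be analyzed using ANCOVA with treatment group as factor and baseline as covariate". For the continuous secondary endpoints other than the radiographic scores, SAP 7.4.2 uses "the ANCOVA model with fixed effects for treatment, and baseline value as a covariate".

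**The concern.** For mTSS, baseline mTSS rank is the score's own baseline. For erosion and joint-space narrowing it is the baseline of a different variable, the total of which each is a part. The SAP gives no reason for treating these two scores differently from the other continuous secondary endpoints, and the repeated wording suggests that the primary model was carried over.

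Two things are at stake, both modest. First, a chance difference between groups in baseline erosion or narrowing is adjusted only so far as it shows in the total. The SAP has no fallback. Section 7.2.2 tests baseline characteristics for imbalance, and 7.2.2.2 includes both component scores, but the follow-on adjusted analyses in 7.4.1.4 cover only ACR20 and mTSS. Second, if change in a component is better predicted by its own baseline than by the total, some precision is given up for nothing.

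**Working it through.** **The plan's own figure.** Protocol 7.1 assumes mTSS changes of 0.5 (150 mg) and 2.0 (placebo), SD 4.0, a two-sided 5% level and 90% power. The difference is 2.0 − 0.5 = 1.5. A two-sample t-test then needs 151 per group (power 0.9011; 0.8992 at 150), as stated. Allowing 10% dropout, 151/0.9 = 167.8, so 168; the plan enrols 170. This rests on an unadjusted test of mTSS, so the covariate for the components cannot alter it. The documents give no power or precision figure for erosion or narrowing.

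**Are the own baselines available?** Yes. SAP 7.2.2.2 summarises both at baseline, and a change score cannot be formed without them.

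**How close are the two covariates?** SAP 6.1.1 describes the reading as "scoring the severity of bone erosion and joint fissure narrowing of the target joints and calculate the total score", so each component is part of mTSS. Let c be the correlation of a component's baseline with baseline mTSS. If the two components have equal SDs and correlate q with each other, c = √((1 + q)/2): q = 0.3 gives 0.81, q = 0.5 gives 0.87, q = 0.8 gives 0.95. A range of 0.80 to 0.95 is therefore reasonable, but it is an assumption.

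**Imbalance.** After adjustment for the total, the part of a chance imbalance in the component that remains has √(1 − c²) of its original SD: √(1 − 0.64) = 0.60 at c = 0.80, √(1 − 0.81) = 0.44 at 0.90, and √(1 − 0.9025) = 0.31 at 0.95. Most of the variance of the imbalance is removed, but not all.

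**Precision.** Let r be the correlation of the component's change with its own baseline. Suppose that change depends on baseline only through that component, which is the case most favourable to own-baseline adjustment. The correlation with mTSS is then c·r, and

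variance ratio (mTSS-adjusted to own-adjusted) = (1 − c²r²)/(1 − r²).

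For example, r = 0.3 and c = 0.80 give (1 − 0.0576)/(1 − 0.09) = 0.9424/0.91 = 1.0356, and √1.0356 = 1.0176. SE ratios:

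| r | c = 0.80 | c = 0.90 | c = 0.95 |
|---|---|---|---|
| 0 | 1.0000 | 1.0000 | 1.0000 |
| 0.1 | 1.0018 | 1.0010 | 1.0005 |
| 0.2 | 1.0075 | 1.0040 | 1.0020 |
| 0.3 | 1.0176 | 1.0094 | 1.0048 |
| 0.4 | 1.0337 | 1.0179 | 1.0092 |
| 0.5 | 1.0583 | 1.0312 | 1.0161 |

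For r up to 0.3 the SE differs by 0 to about 2%. At the top of that range, 151/1.0356 = 145.8, so about 5 subjects per group. At a 90% design point this is about one point of power (0.903 to 0.893, normal approximation).

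**Check on ranks.** The formula is for ordinary ANCOVA. A simulation of the rank ANCOVA (151 per group, skewed baselines, change depending on the component only, c of 0.84 and 0.91) gave SE ratios of 1.000 to 1.007 for rank correlations of 0 to 0.22 between change and own baseline. This is in line with the table.

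**The case against.** A common covariate across a total and its two parts is a defensible choice, and the SAP does set the radiographic scores apart from the general rule. Protocol 7.4.2 says baseline without saying own baseline, and its example is DAS28. Own baseline is the natural reading, but the conflict is one of interpretation. Any imbalance in a component would also be visible in the baseline tables. All of this stands. It supports a sponsor who states a reason for using mTSS, but the SAP states none.

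A reader might infer that the trial is losing appreciable precision because the total must predict a component's change less well than the component's own baseline. The documents do not support this. They give no correlations, and if progression in a component follows total damage, mTSS could serve as well or better. Assumed correlations can be chosen to give a larger figure. With 0.25 to 0.40 for own baseline and 0.15 to 0.30 for mTSS, the pairs 0.25/0.15, 0.35/0.20 and 0.40/0.30 give own-to-mTSS variance ratios of 0.959, 0.914 and 0.923, a reduction of 4 to 9%. But the same ranges run from (1 − 0.40²)/(1 − 0.15²) = 0.859 to (1 − 0.25²)/(1 − 0.30²) = 1.030, so they even allow a loss. Under the component-only model those three pairs imply c = 0.60, 0.57 and 0.75. For two non-negatively correlated components the squared values of c sum to at least 1, so both cannot lie below 0.71. The first two pairs therefore cannot hold for erosion and narrowing together.

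A reader might also take from SAP 7.4.2 that raw follow-up scores go through this model, where the own baseline would matter far more. Footnote 3 of Appendix 2 limits the model to change, so nothing here rests on that reading.

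**Conclusion.** The inconsistency is real. Read literally, the SAP adjusts the erosion and narrowing changes for the baseline of another variable, against the natural reading of the protocol and the SAP's own practice elsewhere, and without a stated reason. The correction brings direct adjustment for chance imbalance in the component and a likely small precision gain for change scores. That gain is about 0 to 2% in SE, given r of at most 0.3, c of 0.80 to 0.95, and change depending on baseline through the component alone. It reaches 3 to 6% only at r = 0.5 with c of 0.80 to 0.90, and it could be nil. None of these inputs can be derived from the documents.

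It should not be read as a threat to validity, since randomisation protects the comparison with either covariate. The two scores are secondary endpoints without multiplicity adjustment, outside the four-step primary testing. The primary mTSS analysis already uses its own baseline rank, and the 151 per group is untouched. This is a minor improvement worth making because it is free.

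**What to change.** In SAP 7.4.2, replace the covariate in the radiographic block with *rank of the corresponding baseline score*: erosion for erosion, joint-space narrowing for joint-space narrowing, mTSS for mTSS. Repeat the covariate in Appendix 2 rows 12.1.1 to 12.1.3 so that the table and the text agree. If the sponsor prefers total mTSS for all three, one sentence giving the reason would do instead.

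The cost is a few words, with no new data and no effect on the primary analysis or sample size. It should be made before unblinding; after that, SAP section 1 requires a change from the planned analysis to be justified in the study report.
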